6.5 TREATMENT GROUPS

The analyses will be conducted by treatment group:

- 1 mg AZ-010
- 3 mg AZ-010
- matching Staccato Placebo (Staccato device without drug coating)

6.6 STATISTICAL HYPOTHESIS TESTS

H₀: There will be no difference between AZ-010 (1 mg or 3 mg) and placebo in the mean number of vomiting/retching events in the 2 hours following treatment.

H₁: Treatment with AZ-010 (1 mg or 3 mg) will result in a statistically significant different mean number of vomiting/retching events versus placebo in the 2 hours following treatment.

6.7 MULTIPLICITY ADJUSTMENT

No adjustments will be made for multiple comparisons for this proof-of-concept study.

6.8 DEFINITION OF SUBGROUPS

No subgroup analyses are planned.

6.9 ENDPOINTS AND ESTIMANDS

6.9.1 PRIMARY ENDPOINT AND ESTIMAND

The mean number of vomiting/retching events in the 2 hours following treatment among those treated for a CVS episode (imminent or otherwise).

6.9.1.1 TARGET POPULATION

The target populations are given by the Efficacy Population which include all participants treated during the Home Treatment Period for a CVS episode (imminent or otherwise). If a PP Population is defined, the primary analysis will be repeated for the PP Population.

6.9.1.2 PRIMARY ENDPOINT

Number of vomiting/retching episodes within two hours following initial treatment, during the Home Treatment Period as assessed at the designated planned two-hour timepoint.

6.9.1.3 HANDLING OF INTERCURRENT EVENTS

- 1. Clinically significant ECG abnormality during the pre-test self-administration which preclude further participation Principal Stratum Strategy:
 - Participants who are excluded from further participation are not included in efficacy analyses, with the population for anticipated use consistent with this exclusion. An underlying assumption is that potential treatment benefit is independent of the likelihood of exclusion for this reason.
- 2. Participant experiences a CVS episode (imminent or otherwise) requiring treatment during the home treatment period Principal Stratum Strategy:
 - The principal stratum of interest is restricted to those participants experiencing at least one episode of CVS (imminent or otherwise) requiring treatment. An underlying assumption is that likelihood of experiencing at least one episode during the Home Treatment Period and severity of CVS

episodes is independent of randomized treatment assignment (and subsequent qualification for the Home Treatment Period).

- 3. Use of rescue medication prior to 2 hours Treatment Policy Strategy:
 - Participants are encouraged not to use rescue prior to 2 hours, however vomiting retching episodes prior to 2 hours will be counted, irrespective of the use of rescue.

6.9.1.4 POPULATION-LEVEL SUMMARY

Mean number of vomiting retching events in the first 2 hours following the initial treatment (during the Home Treatment Period) from an analysis of variance model, with treatment group and randomization strata in the model.

6.9.1.5 MISSING DATA

The necessity and approach to handling missing data for the primary endpoint is dependent upon the extent of missing data and potential reasons for missingness as well as imbalance which may be observed with respect to missing data across treatment groups. A such, post-hoc exploratory analyses may be conducted for this proof-of-concept study to address missing data, including the use of non-missing data from CVS episodes after the first episode to assess treatment benefit.

6.9.2 SECONDARY ENDPOINTS AND ESTIMANDS

Secondary endpoints and associated estimands target the Efficacy Population and PP Population (if defined) and handle intercurrent events 1 and 2 as for the primary estimand and intercurrent event number 3 as for primary (except as noted). Secondary endpoints are described in section 5.8, and population-level summaries are as noted below.

6.9.2.1 POPULATION-LEVEL SUMMARY

The population-level summary for secondary endpoints are defined as follows:

- The intensity of the vomiting/retching attack (Intensity of Attack Scale [IAS]) at 2, 6, 12, and 24 hours following treatment. Participants rate the intensity of their last vomiting/retching episode on a scale of 1 (mild) to 4 (excruciating).
- The Rhodes Index of nausea, vomiting, and retching (RINVR) total score at 6, 12, and 24 hours following treatment.
- The assessment of abdominal pain at 2, 6, 12, and 24 hours following treatment (visual analog scale [VAS] 1-100; 0 = no pain and 100 = worst possible pain).
- The assessment of nausea at 2, 6, 12, and 24 hours following treatment (VAS 1-100; 0 = no nausea and 100 = worst possible nausea).
- The assessment of anxiety/panic at 2, 6, 12, and 24 hours following treatment (VAS 1-100; 0 = no anxiety/panic and 100 = worst possible anxiety/panic).
- The duration of the CVS episode at 24 hours in relation to their typical CVS episodes (Prior Episode Questionnaire [PES]), on a scale where 1=shorter, 2=same duration, and 3=longer.

- The intensity of the CVS episode at 24 hours in relation to their typical CVS episodes (Prior Episode Questionnaire), on a scale where 1=less intense, 2=same intensity, and 3=more intense.
- The proportion of participants requiring rescue medication (anti-emetics, benzodiazapines and triptans) within the 24 hours following treatment with the study medication, as reported either in the ePD or as a concomitant medication.
- The proportion of participants requiring a visit to urgent care, emergency department, or physician's office for care related to the treated episode of CVS within the 24 hours following treatment with the study medication.

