Randomized participants without clinical observations in the 2-hour observation period will be asked to treat a subsequent CVS episode (with single daily dosing up to 5 consecutive days) within 12 weeks after the randomization date. Enrolled participants will self-administer the study medication when they know their CVS episode is imminent or as soon as possible after a CVS-related vomiting episode has begun. Participants will interact with their ePD prior to initiation of treatment (if possible) and to capture the study data. The ePD will be used to record the date and time of study medication administration, the number of vomiting and retching events, and the participant reported outcome measures (including the intensity and duration of the CVS episode, severity of abdominal pain, nausea, and anxiety/panic, and characteristics of the nausea, vomiting and retching over defined time periods) (section 5.8). Participants will also record the number of vomiting and retching events in the 24 hours after dosing on a paper questionnaire.

Participants will be instructed to contact the Research Clinic at the earliest possible time after initiation of dosing and at any time should they require rescue medication, medical assistance or experience an intolerable AE at home during the treatment period. Participants will record rescue medications taken after administration of study medication in their ePD and on a paper concomitant medications form. Rescue medication may include any agent(s) from the list described in Section 9.8 of the protocol. Participants are encouraged to avoid rescue medication for the first 2 hrs. following treatment with the study medication.

Participants will be required to return to the Research Clinic (Visit 3) within 3-5 days from the last study medication administration for final in-clinic assessments, to return the Patient Kit containing the used and unused study medication, ePD, and any other unused supplies. Conversely, participants will be asked to return to the Research Clinic after 12 weeks with their unused Patient Kit if they did not treat a CVS episode within this time period.

Visit 3 will include the following assessments: Vital signs; full physical examination; assessment for treatment emergent adverse events; 12- lead ECG, concomitant medications (including rescue medication taken), and clinical labs.

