5.8.3 SECONDARY ENDPOINTS

All secondary endpoints will be evaluated based on the first vomiting/retching episode.

- The percentage of participants with no vomiting or retching events and no antiemetic benzodiazepine, or triptan rescue medication use in the first 24 hours following treatment. This endpoint will use incorporate data as captured in the 24 hour vomiting and retching questionnaire and the ePD.
- The intensity of the vomiting/retching attack (Intensity of Attack Scale) at 2, 6, 12, and 24 hours following treatment.
- The Rhodes Index of nausea, vomiting, and retching (RINVR) at 6, 12, and 24 hours following treatment.
- The assessment of abdominal pain at 2, 6, 12, and 24 hours following treatment (VAS 1-100; 0 = no pain and 100 = worst possible pain)
- The assessment of nausea at 2, 6, 12, and 24 hours following treatment (VAS 1-100; 0 = no nausea and 100 = worst possible nausea)
- The assessment of anxiety/panic at 2, 6, 12, and 24 hours following treatment (VAS 1-100; 0 = no anxiety/panic and 100 = worst possible anxiety/panic)
- The duration of the CVS episode at 24 hours in relation to their typical CVS episodes (Prior Episode Questionnaire)
- The intensity of the CVS episode at 24 hours in relation to their typical CVS episodes (Prior Episode Questionnaire)
- Use of rescue medication within the 24 hours following treatment with the study medication
- Visit to urgent care, emergency department, or physician's office for care related to the treated episode of CVS within the 24 hours following treatment with the study medication

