8.5 PRIOR AND CONCOMITANT MEDICATIONS

All reported medications will be coded using the World Health Organization-Drug Dictionary (WHODrug version B3, September 2020). A frequency tabulation will be shown by WHO-DD ATC class level 4 and preferred term for the Safety Population for each of following two categories:

- Prior medication: medication received during the 4 weeks (30 days) prior to Screening but is no longer being taken, collected on the CRF page "Prior Medication" at Screening.
- 2) Concomitant medication: medication received during the study, collected on the CRF page "Concomitant Medication".

Concomitant and prior medications will be included in the participant data listing.

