8.1 Inclusion Criteria

- 1. Adult males and females between 18 and 60 years of age, inclusive at the time of signing the informed consent document.
- 2. Understand and voluntarily sign an informed consent document prior to any study related assessments/procedures being conducted.
- 3. Diagnosis of cyclic vomiting syndrome (CVS) using the Rome IV diagnostic criteria and must have:
 - Stereotypical episodes of acute onset vomiting lasting < 1 week;
 - At least 3 discrete episodes of vomiting in the prior year and 2 episodes in the past 6 months, occurring at least 1 week apart;
 - Absence of vomiting between episodes (but milder symptoms may be present);
 - Symptoms must be present for the past 3 months with onset at least 6 months prior
- 4. Has a prodrome or pre-emetic symptoms associated with approximately half of their "typical" CVS episodes
- 5. If of reproductive age, female participants and female partners of male participants, willing and able to use a medically highly effective form of birth control from at least 4 weeks prior to Baseline until at least 30 days following last dose of study drug. Examples of medically highly effective forms of birth control are:
 - Surgical sterility (hysterectomy or bilateral ligation) or post-menopausal (cessation of menses for at least 12 months prior to screening)
 - Sexual partner is sterile, or of the same sex
 - Implants of levonorgestrel in females
 - Oral contraceptive (combined, patch, vaginal ring, injectable, implant) in females
 - Double-barrier method (any combination of physical and chemical methods)
 - Intrauterine device with a failure rate less than 1% per year
- 6. Male participants must:
 - Agree to use, with their partners, one of the highly effective contraceptive methods listed in Inclusion Criterion 5, from Baseline until at least 30 days following last dose of study drug.
 - Refrain from donating sperm during the study and for at least 30 days after the end of the study.

- 7. Otherwise healthy, as determined by the responsible physician, based on a medical evaluation including history, physical examination, vital signs, electrocardiograms (ECGs) and laboratory tests assessed at the screening visit.
- 8. Negative urine tests for selected drugs of abuse and alcohol breath test at Screening.

Note: Patients with a positive urine drug screen for benzodiazepines or opioids may be allowed in the study provided the drug was prescribed by a physician.

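### The SAP takes 24-hour rescue use from different records in two secondary endpoints, and gives no rule for telling rescue from background medication

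*Combined protocol and SAP*

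**What the plan says.** SAP 6.9.2.1 defines the rescue endpoint as the share of participants who need an anti-emetic, benzodiazepine or triptan as rescue in the day after study treatment, "as reported either in the ePD or as a concomitant medication". It has two sources, either of which is enough.

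The responder endpoint in SAP 5.8.3 requires no vomiting or retching and no rescue from the same three classes in the first 24 hours. Its sources are given in one sentence: "This endpoint will use incorporate data as captured in the 24 hour vomiting and retching questionnaire and the ePD". The responder endpoint does not appear in the SAP 6.9.2.1 list, so this sentence is the only derivation it has.

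The form in protocol 17.7 shows what the questionnaire collects: the date of each home dose and the number of events in the following 24 hours. It asks nothing about medication taken.

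On the concomitant record, SAP 8.5 says: "Concomitant medication: medication received during the study, collected on the CRF page" for concomitant medication. SAP 5.3 explains why rescue is found there too: "Participants will record rescue medications taken after administration of study medication in their ePD and on a paper concomitant medications form". Protocol 8.1 adds: "Patients with a positive urine drug screen for benzodiazepines or opioids may be allowed in the study", on condition that a physician prescribed the drug.

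On drug classes, SAP 5.8.3 words the rescue endpoint without a class limit ("Use of rescue medication within the 24 hours following treatment with the study medication"), as does the protocol synopsis. SAP 6.9.2.1 and protocol 12.4.1 limit it to anti-emetics, benzodiazepines and triptans.

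**The concern.** Both endpoints need the same fact about each participant: whether rescue was taken within 24 hours of the first home dose. If they read that fact from different records, the two tables can contradict each other for the same person, and the responder rate can include people who were rescued.

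The second source brings a further problem. The concomitant record mixes rescue with everything else taken on study. The SAP sets no condition on when a drug was taken relative to the home dose, what it was for, or whether it was scheduled or as needed. Two competent programmers could build different rescue flags, and the choice might be made after treatment codes are known.

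**Working it through.** **Plan's own figure.** SAP 6.2 plans 3 × 50 = 150 participants and states that this does not rest on a power calculation. No rescue rate is given, so there is no figure for this endpoint to reproduce.

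**Step 1: the two derivations side by side.** Take a participant with no events in 24 hours.

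| What happened | Rescue endpoint (SAP 6.9.2.1) | Responder endpoint (SAP 5.8.3 sources) |
|---|---|---|
| Rescue in ePD and on paper | Rescued | Not a responder |
| Rescue in ePD only | Rescued | Not a responder |
| Rescue on paper form only | Rescued | Can be a responder |
| No rescue; scheduled prescribed benzodiazepine on the concomitant record | Rescued if matched on class alone; otherwise not | Responder |

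The third row follows directly from the stated sources. The fourth depends on how the SAP is programmed. A participant with any event is a non-responder whatever the rescue record shows, so the responder table is affected only among those with zero events.

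**Step 2: size per participant.** With 50 per arm, one misclassified participant shifts that arm's rate by 1/50 = 2 percentage points. The documents do not say how many will have paper-only rescue.

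**Step 3: size if background use were scored as rescue.** Let m be the share in each arm scored as rescued on background use alone. Assume m is equal across arms and independent of true rescue, and that the treatment effect is the same in these participants as in the rest. Then

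p′ = m + (1 − m)p, so p′₁ − p′₂ = (1 − m)(p₁ − p₂).

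Example with assumed true rates of 50% on placebo and 25% on active, and m = 10%:
- Placebo: 0.10 + 0.90 × 0.50 = 0.550.
- Active: 0.10 + 0.90 × 0.25 = 0.325.
- Difference: 22.5 points = 0.90 × 25.

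Approximate power (unstratified, two-sided 0.05) is Φ{(d − 1.96√[2p̄(1 − p̄)/n]) / √[(p₁(1 − p₁) + p₂(1 − p₂))/n]}. At m = 0 and n = 50 this is (0.25 − 1.96 × 0.0968)/0.0935 = 0.64, giving 74%. The same formula gives:

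| Assumed true rescue, placebo vs active | n per arm | m = 0 | m = 10% | m = 20% | m = 30% |
|---|---|---|---|---|---|
| 50% vs 25% | 50 | 74% | 62% | 52% | 42% |
| 60% vs 35% | 50 | 71% | 62% | 53% | 44% |
| 40% vs 20% | 50 | 59% | 46% | 36% | 29% |
| 50% vs 25% | 35 | 58% | 47% | 38% | 31% |

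The rescue rates and m are assumptions. So is n = 35, which allows for participants who treat no episode and are excluded from efficacy under SAP 6.1.

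**Step 4: drug classes.** Protocol 9.8 also permits an antihistamine, analgesics and acid suppressants as rescue. A participant who takes only ibuprofen counts under the SAP 5.8.3 wording and does not count under SAP 6.9.2.1.

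**The case against.** A reader might infer that the SAP counts every anti-emetic, benzodiazepine or triptan on the concomitant medication page, so that all maintenance users are scored as rescued and the contrast is necessarily diluted. The documents do not support that. SAP 6.9.2.1 speaks of participants requiring rescue, and the closing phrase says where rescue is reported. SAP 5.3 and protocol 9.7 describe rescue as something taken after study dosing, and the paper form as a second place to write it. Automatic scoring is one possible reading. Permitted background use is documented only for prescribed benzodiazepines, and a positive urine screen does not establish daily scheduled use. Maintenance anti-emetics and triptans are neither expressly allowed nor excluded, and the prohibited list mentioned in protocol 9.7 is not given. This objection stands. What remains is that no rule rules the broad reading out.

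On sources, SAP 5.8.3 does not say that its two are the only ones, and protocol 9.7 requires every rescue dose to be entered in the ePD. With perfect entry the endpoints would agree. But the either/or wording in SAP 6.9.2.1 already allows for rescue found in only one place, and the responder text does not.

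On classes, the SAP 5.8.3 wording can be read as a short label completed by SAP 6.9.2.1, and the SAP overrides the protocol's statistical text. That makes this a wording repair.

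On consequence, these are two of ten secondary endpoints in a proof-of-concept study with no multiplicity control. The primary endpoint counts events irrespective of rescue.

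**Conclusion.** The inconsistency of sources is real and does not depend on any assumed rate: as written, a participant with paper-only rescue is rescued in one endpoint and can be a responder in the other. Its size depends on the number of zero-event participants with paper-only rescue, at 2 points per participant in an arm of 50. That number is unknown, and the direction of any effect on the treatment contrast cannot be settled from the documents.

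The possible scoring of background use is missing detail. The factor (1 − m) and the power figures show only what a class-only match would cost under the stated assumptions. They are no estimate of what will happen in this trial, and at m = 0 nothing is lost. The point bears on the rescue and responder endpoints only.

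**What to change.** Before unblinding, add to SAP 6.9.2.1 one participant-level rescue flag built from the ePD plus the concomitant medication records, and use it for both the rescue endpoint and the responder endpoint in SAP 5.8.3.

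- Count a record in the three classes only if a dose was taken within 24 hours after the first home dose, as rescue or for the treated CVS episode.
- Include as-needed doses of a drug the participant already had. Protocol 9.8 bases the choice of rescue on the patient's preference and experience, so excluding drugs by an earlier start date could remove true rescue.
- Do not count scheduled background doses.
- Settle records with unclear time or purpose by blinded review.
- Add a sensitivity analysis that counts every record in the three classes.
- Align the rescue endpoint wording in SAP 5.8.3 with the three-class definition in SAP 6.9.2.1 and protocol 12.4.1.

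The cost is a small amount of programming and blinded record review. The documents do not show whether the concomitant medication page holds dose times or indications. If it does not, more records will go to review. No trial procedure changes.

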6.10 MAIN ANALYTICAL APPROACH

Data from the RINVR, IAS, VAS, and PES will be analyzed using a mixed model for repeated measures (MMRM). Fixed effects will include treatment group, timepoint, randomization strata, and a treatment-by-timepoint interaction. Timepoint will be fit as a repeated effect using the repeated statement in SAS. An unstructured covariance structure and Kenward-Roger degrees of freedom will be used. In the event an unstructured covariance structure fails to converge, a Toeplitz structure will be used.

Least squares means will be presented for treatment*timepoint, with the significance level of the treatment-by-timepoint interaction presented in summary tables. Pair-wise comparisons of differences in LS means, two-sided 95% confidence intervals (CIs) on differences, and p-values will be provided for each active treatment versus placebo for each timepoint.

Proportion data (ie, rescue medication or visits to urgent care/ER/doctor will be analyzed using a Mantel-Haenszel test, stratifying on randomization strata, in a pairwise fashion of each dose versus placebo.

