5.7 RANDOMIZATION

Participants will be randomized in a 1:1:1 ratio to 1 mg AZ-010, 3 mg AZ-010, or matching Staccato Placebo (Staccato device without drug coating). Randomization will be stratified by duration of the participant's typical CVS episode into one of the following two categories:

- 1. Typical episode of CVS lasts 24 hrs. or less from the first vomiting/retching event
- Typical episode of CVS lasts greater than 24 hrs. from the first vomiting/retching event.

The randomization schedule will be generated prior to study start. All study participants, Investigators, and site study staff will be blinded to study medication assignment. Devices and packaging of AZ-010 and placebo are identical in appearance.

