5.8.1.3 VISUAL ANALOG SCALE (VAS)

The visual analog scale is a scale of continuous measure initially developed for pain that has been used in a variety of clinical settings where the endpoint of interest is based on a subjective perception. The visual analog scale is a distinct 100-millimeter line anchored on the left end (0) at no degree of impairment and on the right end (100) at full degree of impairment, where indication of the degree of impairment perceived at the time of assessment is captured by marking the appropriate position on the line Statistical Analysis Plan: Final Version 1.0, 03 March 2022

between the anchor points. The measured distance of the mark from the left anchor is recorded in millimeters and this scale is adapted for the ePD.

There are 3 different VAS scales assessed in the study. In each case the participant is asked to rate the appropriate variable in relation to their last vomiting/retching episode:

- The assessment of abdominal pain whereby 0 = no pain and 100 = worst possible pain;
- The assessment of nausea whereby 0 = no nausea and 100 = worst possible nausea;
- The assessment of anxiety/panic whereby 0 = no anxiety/panic and 100 = worst possible anxiety/panic.

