5.8.1.5 INTENSITY OF ATTACK SCALE

The Intensity of Attack scale is designed to assess the severity of the last vomiting/retching episode at the time of assessment. Severity ranges from Mild to Excruciating on a 4 point scale. This scale is administered on the ePD and participants are prompted to answer the questions according to the Schedule of Events.

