6 STATISTICAL ANALYSES

6.1 GENERAL CONSIDERATIONS

All analysis dataset preparations and statistical analyses will be performed using SAS[®] version 9.4 or higher. No imputation will be performed for missing data unless stated otherwise.

Data will be summarized by dosing group (1 mg AZ-010, 3 mg AZ-010, placebo). All data for analysis will be listed by participant.

The same number of decimal places as in the raw data will be presented when reporting minimum and maximum, 1 more decimal place than in the raw data will be presented when reporting mean and standard deviation.

Continuous variables will be summarized by treatment using descriptive statistics (n, mean, median, standard deviation, minimum, and maximum). For categorical variables, frequencies and percentages will be presented by treatment. Baseline is defined as the last observation prior to initiation of Study Medication.

Listings for CSR Appendix 16.2 will include all the participant data points being collected or derived for analyses. Data listings will be provided for all participants up to the point of study completion or withdrawal.

All statistical tests will be 2-sided with a significance value of 0.05. Participants will generally be summarized by actual treatment received.

If the 12-week treatment period has expired and participants have not yet treated a CVS episode, they will be excluded from efficacy analyses since they did not receive any study medication specifically in anticipation of a CVS episode.

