6.2 SAMPLE SIZE DETERMINATION

This is a proof-of-concept study. There are no studies in the literature to provide reliable estimates of active treatment or placebo response rates using vomiting/retching events, or the estimate of variances around these measures, in participants with CVS being treated acutely with an abortive therapy. Consequently, sample size was not based on power calculations.

Approximately 150 participants will be randomized to 1 of 3 treatment groups. An N of 50 per group should be sufficient to describe and compare across the efficacy parameters.

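### The Toeplitz fallback for the MMRM does not say whether variances may differ by timepoint; read the usual SAS way it pools them, which can distort per-timepoint standard errors if the fallback is used.

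*Combined protocol and SAP*

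**What the plan says.** SAP 6.10 analyses RINVR, IAS, VAS and the Prior Episode Questionnaire with an MMRM fitted through the SAS REPEATED statement. The first-choice covariance is unstructured, with Kenward-Roger degrees of freedom. The only alternative is: "In the event an unstructured covariance structure fails to converge, a Toeplitz structure will be used". The SAP does not say whether this Toeplitz matrix has a common variance or a separate variance at each timepoint. It gives no further step and names no empirical (sandwich) variance estimator.

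The reported results are differences in LS means, 95% confidence intervals and p-values for each dose against placebo at each timepoint. SAP 6.1 sets the level: "All statistical tests will be 2-sided with a significance value of 0.05".

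SAP 6.9.2.1 gives the assessment times. The IAS line reads "The intensity of the vomiting/retching attack (Intensity of Attack Scale [IAS]) at 2, 6, 12, and 24 hours following treatment", and the three VAS lines use the same times. RINVR is at 6, 12 and 24 h. The Prior Episode Questionnaire is at 24 h only.

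SAP 6.2 states that no reliable variance estimates exist for this setting and adds: "Consequently, sample size was not based on power calculations".

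**The concern.** In SAS, plain Toeplitz is TYPE=TOEP: one variance for all timepoints and one correlation per lag. The version with a separate variance at each timepoint has its own name, TYPE=TOEPH. A programmer working from SAP 6.10 would most naturally code TOEP.

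That matters because the outputs are read one timepoint at a time, and the standard error of a contrast at one timepoint depends directly on the variance assumed there. If a common variance is imposed on data whose spread changes, some timepoints get intervals that are too narrow and others get intervals that are too wide. Kenward-Roger does not repair a misspecified variance.

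The documents give some reason to doubt equal spread. Protocol 4.1 describes vomiting that peaks in the first hour and then declines. In protocol appendix 17.3 the RINVR recall period lengthens from 4 h (at the 6 h assessment) to 6 h (at 12 h) and 12 h (at 24 h).

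**Working it through.** The plan states no SD, correlation or standard error for these scales, so there is no figure of its own to reproduce. The check asks what a common-variance Toeplitz fit does to timepoint standard errors under assumed spreads.

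**Inputs from the documents.** Two-sided 0.05 (SAP 6.1); about 50 randomised per arm, 1:1:1 (SAP 5.7 and 6.2); times 2, 6, 12 and 24 h (SAP 6.9.2.1).

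**Assumed inputs.** SDs by timepoint, on a 0–100 scale, as listed below; correlation 0.97 to the power of the gap in hours. A base of 0.93 gives nearly the same results.

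**Method.** For a true covariance S, take the homogeneous Toeplitz matrix M that minimises log|M| + tr(M⁻¹S), which is where a Gaussian likelihood fit settles in large samples. With complete data and equal arms:

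- SE of a difference at time t = SD_t × √(2/n), so SE ratio = (pooled Toeplitz SD) / (true SD at t). The sample size cancels.
- Actual type I error = 2 × [1 − Φ(1.96 × ratio)].

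**Results at 2/6/12/24 h.**

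| Assumed SDs | Pooled SD | SE ratio | Type I error, % |
|---|---|---|---|
| 25/25/25/25 | 25.00 | 1.00/1.00/1.00/1.00 | 5.0/5.0/5.0/5.0 |
| 27/26/25/23 | 25.18 | 0.93/0.97/1.01/1.10 | 6.8/5.8/4.8/3.2 |
| 30/28/24/18 | 25.01 | 0.83/0.89/1.04/1.39 | 10/8/4/0.6 |
| 20/25/25/30 | 25.36 | 1.27/1.01/1.01/0.85 | 1.3/4.7/4.7/9.8 |

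Worked line for 30/28/24/18. At 2 h the ratio is 25.01/30 = 0.83, and 2 × [1 − Φ(1.96 × 0.834)] is about 10%. At 24 h it is 25.01/18 = 1.39, which gives about 0.6%. With 50 per arm, √(2/50) = 0.2. The Toeplitz SE is then 25.01 × 0.2 = 5.0 at every timepoint, whereas the correct SE is 30 × 0.2 = 6.0 at 2 h and 18 × 0.2 = 3.6 at 24 h. The 95% half-width would be 1.96 × 5.0 = 9.8 in both places, instead of 11.8 and 7.1.

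**Missing data.** A simulation with two arms of 50, monotone dropout and 400 runs per scenario used maximum likelihood and a t reference, not SAS REML with Kenward-Roger. The simulation error at 5% is √(0.05 × 0.95/400) = 0.011. Rejection rates at 2/6/12/24 h were:

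- Equal SDs: Toeplitz 0.050/0.042/0.035/0.040; unstructured 0.050/0.035/0.035/0.048.
- SDs 20/25/25/30: Toeplitz 0.012/0.038/0.050/0.115; unstructured 0.045/0.048/0.058/0.058.

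**Which constraint does the damage.** The equal-SD row uses correlations that depend on the uneven 4, 6 and 12 h gaps, so equal correlation per lag is wrong there; the SE ratio is still 1.00. The pooled variance causes the error.

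**Covariance parameters for k timepoints.** Unstructured k(k+1)/2, TOEPH 2k−1, TOEP k. At four timepoints that is 10, 7 and 4; for RINVR (three) it is 6, 5 and 3.

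**The case against.** The case against has several parts, and most of it stands as a limit on the point.

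*The SAP does not specify a common variance.* A reader might infer that the plan commits to homogeneous Toeplitz. It says only Toeplitz; the common variance comes from SAS naming. If the sponsor meant the heterogeneous form, the sentence is under-specified and the same edit settles it.

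*Non-convergence may never happen.* A reader might infer that the fallback is likely, because the VAS asks participants to "rate the appropriate variable in relation to their last vomiting/retching episode" and the IAS is "designed to assess the severity of the last vomiting/retching episode at the time of assessment". Someone whose vomiting has stopped would rate the same event again at 12 and 24 h, making those columns nearly collinear. The documents do not show this, and the argument undercuts the larger error figures: repeated ratings pull the 12 and 24 h SDs together. With SDs 30/28/24/24 and a 12–24 h correlation of 0.95–0.98, type I error is only about 7.8/5.9/2.8/2.8%. In a separate check with SDs 30/28/24/18, three arms and 10% missing at each later timepoint, an unstructured maximum-likelihood fit converged in 60 of 60 runs at each of 50, 30, 20 and 15 per arm. That is not SAS REML, but it gives no support for calling failure likely.

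*Uneven spacing is harmless on its own.* A reader might infer that giving the 2–6 h and 12–24 h pairs the same correlation distorts the standard errors. It does not with complete data, and the missing-data simulation showed no visible inflation.

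*The direction is unknown.* Rising SDs move the inflated error from the early to the late timepoints.

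*The stakes are low.* These are secondary endpoints in a proof-of-concept study with no multiplicity adjustment (SAP 6.7).

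What remains is that, whenever the fallback is used, the natural coding adds an equal-variance assumption that the plan does not justify and need not make.

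**Conclusion.** The point holds as a minor, conditional improvement. Three things must coincide for harm: the unstructured fit fails, the fallback is coded as TYPE=TOEP, and variances differ materially between timepoints. Under those conditions the illustrative type I error ranges from a slight departure (3.2% to 6.8% with SDs 27/26/25/23) to a clear one (0.6% to 10% with 30/28/24/18; 1.3% to 9.8% with 20/25/25/30). With equal variances there is none. All SDs and correlations are assumptions, and the table rests on complete data and a large-sample approximation.

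It would go too far to say that the plan's standard errors are wrong: the unstructured model with Kenward-Roger is a sound first choice. The issue reaches IAS, VAS and RINVR only. The Prior Episode Questionnaire has a single 24 h timepoint, so it has no repeated-measures covariance to choose, and the primary endpoint uses an ANOVA (SAP 6.9.1.4).

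**What to change.** In SAP 6.10, replace the fallback sentence with an ordered rule:

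1. If the unstructured fit does not converge, refit it in Cholesky form (TYPE=FA0(k), k = number of timepoints). This is the same unstructured model in a parameterisation that is often easier to fit.
2. If that also fails, use heterogeneous Toeplitz (TYPE=TOEPH) in place of homogeneous Toeplitz.

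The cost is one sentence in the SAP and a few more covariance parameters in a model that may never be run: 7 against 4 at four timepoints, and 5 against 3 for RINVR. Fixing the order before unblinding also rules out choosing a covariance structure after the results are seen. An empirical variance estimator would be another route, but the SAP would then also have to state the degrees-of-freedom method.
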